# *Note: A documented fever and feeling feverish will count as one point on the cumulative symptom score.*

Signs and symptoms will also be collected via the FLU-PRO and Validation Diary instrument which will be completed once daily after 3:00 pm through confinement. Subjects will continue to complete the FLU-PRO daily after discharge through Day 15. The modified Jackson score and FLU-PRO will be compared in exploratory analyses.

• Component signs and symptoms of the FLU-PRO and Validation Diary include runny/dripping nose, congested/stuffy nose, sinus pressure, scratchy or itchy throat, sore or painful throat, difficulty swallowing, teary or watery eyes, sore or painful eyes, eye sensitivity, trouble breathing, chest congestion, chest tightness, dry or hacking cough, wet or loose cough, nausea, stomach ache, dizziness, head congestion, headache, lack of appetite, excessive sleepiness, body aches or pains, weakness or tiredness, chills or shivering, feeling cold, feeling hot, and sweating.

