3.2.5. Symptom Scores

The cumulative Modified Jackson Score (MJS; see [Figure 4](#)) will be calculated as described in [Section 3.2.1](#).

The area under the MJS curve will be calculated for each participant from Day 2 through Day 8, for uninfected participants (see [Section 3.2.3](#)), or from the first RT-PCR+ day through the last, for infected participants; this calculation will be made as described above in [Section 3.2.4](#) for total viral shedding, except in this case scaled by the number of days over which symptoms are summed.

The FLU-PRO total severity score is defined as the mean score across all 32 items (see [Figure 5](#)), with component scores ranging from 0 to 4. Six domain scores are also computed as mean scores, representing symptom severity in each body system. Scores will be computed for each study day utilizing the maximum severity score per symptom, and cumulative FLU-PRO scores (for the total FLU-PRO score and component scores) will be computed as the sum of the daily scores over the relevant time period.

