4.6.1. Clinical Variables

Clinical variables such as viral detection, viral shedding, and solicited symptoms and laboratory findings that are a part of the definition of symptomatic influenza virus infection, are assessed at each study day during the confinement period, after the day of study challenge. Symptoms are also assessed in the clinic visit on Day 15.

Virologic assessments are done at screening (Days -45 to -3), baseline (Days -2 and -1), and then repeated daily from Days 2-8 during the confinement period or for a longer period if still RT-PCR positive for influenza on Days 7 or 8 until two negative swabs are confirmed, at least 12 hours apart, consecutively. Only qualitative RT-PCR is performed at the screening visit, but subsequently nasopharyngeal (NP) swab samples are collected for quantitative RT-PCR as well. Quantitative RT-PCR (qRT-PCR) will be conducted by a research laboratory at Duke University. Qualitative RT-PCR is conducted via multiplex respiratory virus assay (BIOFIRE® FILMARRAY® respiratory panel by bioMérieux or Luminex xTAG®) on NP swabs at the local clinical site. Qualitative and quantitative RT-PCR for influenza from NLF specimens and quantitative viral culture from NP swabs and/or NLF specimens may be performed as well; these would be analyzed subsequently to compilation of the primary CSR, if the assays are performed.

Symptomatic influenza infection is assessed using a Modified Jackson score (MJS) collected by study staff twice a day (approximately 8 AM and after 3 PM) from Day -2 until the time of discharge, and again at the Day 15 visit to assess any ongoing symptoms. [Figure 4](#) displays the MJS investigator tool for assessing symptoms. Fever and lymphopenia, both included among the MJS symptoms for determining the symptomatic influenza attack rate, are assessed separately from the MJS form.

An additional validated, patient-reported outcome (PRO) measure to standardize assessment of influenza symptoms in clinical research (i.e., FLU-PRO Survey Instrument and Validation Diary) is to be completed by participants once a day (after 3:00 PM) from Day -2 through Day 15. The investigators review the FLU-PRO and Validation Diary at the Day 15 visit to assess any ongoing symptoms. The FLU-PRO questionnaire is presented in [Figure 5](#) for reference.

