5. GENERAL STATISTICAL CONSIDERATIONS

5.1. General Principles

The challenge period is defined as the day of study challenge (Day 1) through discharge from the confinement period (Day 8 or later).

Continuous variables will generally be summarized using the following descriptive statistics: non-missing sample size (denoted by “n”), mean or geometric mean, standard deviation, minimum, median, and maximum. Titers will be summarized with geometric means, first across replicates to compute one value for each individual sample and then across participants within clinical outcome groups. The frequencies and percentages (based on the non-missing sample size) of observed levels will be reported for categorical measures. Data listings will typically be sorted by site or other grouping variable (e.g. infection status), participant, and by visit number within participant, where appropriate. All tables will be annotated with the total population size relevant to that table, including any missing observations.

For continuous variables, confidence intervals will be computed based on the t-distribution, unless the data appear especially non-normal and the sample sizes for the analysis are insufficient to apply the central limit theorem. Bootstrap confidence intervals may be calculated instead if the t-distribution is determined to be unsuitable. For binary variables, confidence intervals will be computed using the exact Clopper-Pearson method.

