7. Participants will remain in the confinement unit for a minimum of seven days after the date of challenge. Participants will leave the unit after they meet the following discharge criteria: two consecutive negative NP swabs collected 12 hours apart (that are performed on Study Day 6 or thereafter) for influenza A by qualitative RT-PCR performed by the local clinical laboratory, are afebrile (< 100.6°F/38.1°C), have SpO₂ ≥ 95% on room air, show no moderate or severe influenza signs or symptoms by clinical evaluation, and are clinically and hemodynamically stable for 48 hours. Participants who do not meet discharge criteria on Study Day 8 will remain in the confinement unit until the criteria are met. Study procedures for the confinement unit will be the same as on Study Day 8, except for no NLF collection or additional blood draws unless clinically indicated.
8. A treatment course of oseltamivir phosphate or baloxavir marboxil will be provided to all participants who do not have two consecutive negative NP swabs by qualitative RT-PCR for influenza by Study Day 6. Treatment will begin as early as Study Day 6, or thereafter if indicated, or earlier if terminates study prior to Study Day 8.
9. Height and weight will be measured at Screening.
10. Concomitant medications taken within 90 days prior to signing the ICF are collected.
11. Clinical evaluation (including oral/pharyngeal, neck, lung and heart exam), and symptom evaluation daily while in the confinement unit. An otoscopic exam will be performed at baseline and as needed.
12. Oral temperature, blood pressure, pulse, and respiratory rate will be assessed approximately every 8 hours while in the confinement unit (from 12:00AM – 11:59PM), while the participants are awake, and as clinically indicated.
13. Peripheral oxygen saturation (SpO₂) on room air at screening, on admission, and when oral temperature, blood pressure, pulse, and respiratory rate are assessed through the confinement period and at follow-up visits.
14. Self-assessment using FLU-PRO and Validation Diary to be performed after 3:00 pm on the Day -2 and after 3:00 pm each day of confinement and through Day
15. Modified Jackson Score to be obtained on the evening of Day -2 and in the morning and afternoon of each day of confinement (Approximately at 8:00 AM and after 3:00 PM) and on Day 15 during visit. Assure AM assessment on Study Day 1 is performed pre-challenge.

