Cumulative FLU-PRO (Eyes)	Mean (95% CI)	x.x (x.x, x.x)	x.x (x.x, x.x)	x.x (x.x, x.x)	x.x (x.x, x.x)	x.x (x.x, x.x)	x.x (x.x, x.x)	x.x (x.x, x.x)	x.x (x.x, x.x)	x.x (x.x, x.x)	x.x (x.x, x.x)	x.x (x.x, x.x)	x.x (x.x, x.x)
	Minimum	XX	XX	XX	XX	XX	XX	XX	XX	XX	XX	XX	XX
	Median	XX	XX	XX	XX	XX	XX	XX	XX	XX	XX	XX	XX
	Maximum	XX	XX	XX	XX	XX	XX	XX	XX	XX	XX	XX	XX
Cumulative FLU-PRO (Chest/Respiratory)	Mean (95% CI)	x.x (x.x, x.x)	x.x (x.x, x.x)	x.x (x.x, x.x)	x.x (x.x, x.x)	x.x (x.x, x.x)	x.x (x.x, x.x)	x.x (x.x, x.x)	x.x (x.x, x.x)	x.x (x.x, x.x)	x.x (x.x, x.x)	x.x (x.x, x.x)	x.x (x.x, x.x)
	Minimum	XX	XX	XX	XX	XX	XX	XX	XX	XX	XX	XX	XX
	Median	XX	XX	XX	XX	XX	XX	XX	XX	XX	XX	XX	XX
	Maximum	XX	XX	XX	XX	XX	XX	XX	XX	XX	XX	XX	XX
Cumulative FLU-PRO (Body/Systemic)	Mean (95% CI)	x.x (x.x, x.x)	x.x (x.x, x.x)	x.x (x.x, x.x)	x.x (x.x, x.x)	x.x (x.x, x.x)	x.x (x.x, x.x)	x.x (x.x, x.x)	x.x (x.x, x.x)	x.x (x.x, x.x)	x.x (x.x, x.x)	x.x (x.x, x.x)	x.x (x.x, x.x)
	Minimum	XX	XX	XX	XX	XX	XX	XX	XX	XX	XX	XX	XX
	Median	XX	XX	XX	XX	XX	XX	XX	XX	XX	XX	XX	XX

Symptom Score	Statistic	10 ⁴ TCID ₅₀ Challenge Virus (N=X)			10 ⁵ TCID ₅₀ Challenge Virus (N=X)			10 ⁶ TCID ₅₀ Challenge Virus (N=X)			Sham Inoculum (N=X)		
		Infected ^a	Uninfected	All Participants in Dose Group	Infected ^a	Uninfected	All Participants in Dose Group	Infected ^a	Uninfected	All Participants in Dose Group	Infected ^a	Uninfected	All Participants in Dose Group
	Maximum	XX	XX	XX	XX	XX	XX	XX	XX	XX	XX	XX	XX
Cumulative FLU-PRO (Gastrointestinal)	Mean (95% CI)	x.x (x.x, x.x)	x.x (x.x, x.x)	x.x (x.x, x.x)	x.x (x.x, x.x)	x.x (x.x, x.x)	x.x (x.x, x.x)	x.x (x.x, x.x)	x.x (x.x, x.x)	x.x (x.x, x.x)	x.x (x.x, x.x)	x.x (x.x, x.x)	x.x (x.x, x.x)
	Minimum	XX	XX	XX	XX	XX	XX	XX	XX	XX	XX	XX	XX
	Median	XX	XX	XX	XX	XX	XX	XX	XX	XX	XX	XX	XX
	Maximum	XX	XX	XX	XX	XX	XX	XX	XX	XX	XX	XX	XX

Notes: N = Number of participants in the Safety population; GMT = Geometric Mean Titer; GMFR = Geometric Mean Fold-Rise. Cumulative FLU-PRO scores are the sum of the daily scores (based on maximum severity per question) across the entire challenge period.

^a RT-PCR+ results reported on at least two days during the challenge period (Days 2 to 8).

^b Confidence interval calculated based on the Student's t-distribution.

Table 44: Maximum Severity of Influenza Symptoms Reported During the Challenge Period by Clinical Site, Infected Participants in the Safety Population

Symptom	Severity	Duke University (N=X)		University of Maryland (N=X)	

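### Cumulative FLU-PRO in SAP Table 43 is summed to discharge rather than over common days, so a longer stay can raise the score at equal daily severity

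*SAP*

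**What the plan says.** **The sum.** SAP 3.2.5 defines the cumulative FLU-PRO score (total and components) as "computed as the sum of the daily scores over the relevant time period" and does not name the period. The Table 43 note does: "Cumulative FLU-PRO scores are the sum of the daily scores (based on maximum severity per question) across the entire challenge period". Neither place scales the sum by the number of days.

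**The period.** SAP 5.1: "The challenge period is defined as the day of study challenge (Day 1) through discharge from the confinement period (Day 8 or later").

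**What ends it.** Footnote 7 of the Schedule of Activities (SAP Table 1) requires "two consecutive negative NP swabs collected 12 hours apart", together with clinical conditions: no fever, adequate oxygen saturation, no moderate or severe influenza signs or symptoms, and 48 hours of stability. It adds: "Participants who do not meet discharge criteria on Study Day 8 will remain in the confinement unit until the criteria are met".

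**What is collected.** Under SAP 4.6.1 the FLU-PRO "is to be completed by participants once a day (after 3:00 PM) from Day -2 through Day 15". Protocol 4.1 confirms that participants "complete the FLU-PRO daily after discharge through Day 15". The diary days are therefore the same for everyone, discharged or not.

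**The neighbouring scores.** In the same table, the maximum cumulative Modified Jackson Score (MJS) comes from 5-day windows inside Days 2 to 8 (Table 14), and the MJS area under the curve is divided by the number of days (SAP 3.2.5).

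**The concern.** Table 43 compares cumulative FLU-PRO by infection status and dose group. The number of days entering the sum is set by the discharge date. That date depends on shedding, which is the stratifying variable, and on symptoms, which are the outcome being summed. A symptom on Day 9 counts for a participant still in the unit. The same symptom on the same day, recorded in the same diary, does not count for a participant discharged on Day 8.

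Differences between columns of Table 43 could then partly measure time in the unit. The comparison with MJS, which is the purpose of SAP 7.2.1, would also set one instrument on a discharge-dependent window beside another on fixed 5-day windows.

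**Working it through.** The documents give no figure for this point, so there is nothing to reproduce. The check has two parts: which window applies, and how much it matters.

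**1. Which window applies**

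- SAP 5.1, the general definition: Day 1 to discharge, Day 8 or later.
- Table 43 note on FLU-PRO: the entire challenge period, with no days given.
- Table 43 footnote a: the challenge period as Days 2 to 8, attached only to the Infected columns.
- Table 28 footnote a: the challenge period as Days 2 to 8+.
- Table 37, the FLU-PRO shell by study day: a separate column for Days 9 and later.

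The general definition governs, and other shells expect stays past Day 8. Footnote a conflicts with SAP 5.1 and Table 28 and does not define the FLU-PRO sum.

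**2. Size for one participant**

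Let x_d be the daily FLU-PRO score on Day d and D the discharge day.

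Score(D) = x_1 + ... + x_D. Inflation relative to Day 8 = Score(D)/Score(8) - 1.

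*Case A: constant daily severity s (assumption).* Score(D) = D × s, so inflation = D/8 - 1.

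- Day 9: 9/8 - 1 = 12.5%
- Day 10: 10/8 - 1 = 25%

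These are the largest values as long as the average score after Day 8 is no higher than the average up to Day 8.

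*Case B: one declining course, identical for everyone (assumption).* Daily scores from Day 1 to Day 15: 0.10, 0.30, 0.70, 0.90, 0.70, 0.50, 0.35, 0.25, 0.20, 0.15, 0.10, 0.08, 0.05, 0.03, 0.02.

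- Day 8: 3.80
- Day 9: 3.80 + 0.20 = 4.00, and 4.00/3.80 - 1 = 5.3%
- Day 10: 4.00 + 0.15 = 4.15, and 4.15/3.80 - 1 = 9.2%

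*Case C: no symptoms after Day 8.* Inflation = 0%.

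Daily scores cannot be negative, so the direction is never downward. SAP 4.1 plans confinement to Day 10; footnote 7 of Table 1 sets no cap.

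**3. Size for a group mean**

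The documents give no distribution of stays. Assume a fraction p leaves on Day 10 and the rest on Day 8, with identical symptom courses. The group mean then rises by p × 25% (Case A) or p × 9.2% (Case B):

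- p = 0.2: 5.0% or 1.8%
- p = 0.5: 12.5% or 4.6%

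**4. Checking the possible remedies on the Case B course**

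| Definition | Discharge Day 8 | Day 9 | Day 10 |
|---|---|---|---|
| Sum to discharge | 3.80 | 4.00 (+5.3%) | 4.15 (+9.2%) |
| Mean per day to discharge | 3.80/8 = 0.475 | 4.00/9 = 0.444 (-6.4%) | 4.15/10 = 0.415 (-12.6%) |
| Sum over Days 2-8 | 3.70 | 3.70 | 3.70 |
| Sum over Days 2-15 | 4.33 | 4.33 | 4.33 |

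A per-day mean over the stay reverses the bias and, on this course, enlarges it. It is neutral only if severity is constant. Only a window common to all participants removes the dependence on length of stay.

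**The case against.** **The window may already be fixed.** Footnote a of Table 43 reads the challenge period as Days 2 to 8. If a programmer applies that to the FLU-PRO sum, the problem disappears. What stands is that the SAP is inconsistent. The footnote belongs to the Infected flag, so it does not settle the FLU-PRO window, and two programmers could derive different totals.

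**A longer stay partly reflects real illness.** Discharge also requires clinical recovery, and a cumulative score is meant to include duration. This is fair, but a common window with the diary already collected to Day 15 measures duration equally for all. A window ending at discharge does not.

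**Late scores may be low.** Antiviral treatment can start from Day 6 (Table 1, footnote 8), and symptoms usually decline. This stands; it is why Cases B and C are shown beside Case A.

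**The consequence is small.** Table 43 is exploratory, descriptive, without p-values and not marked for the topline report. Tables 37-40 and Figures 11 and 13 already show FLU-PRO by study day. This also stands.

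**Stronger readings that the documents do not support.**

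- A reader might infer that infected participants are always summed over more days. Those who clear and recover by Day 8 leave then. Uninfected participants can also stay, because that group includes people with one positive day and because PCR is only one of the discharge criteria.
- A reader might infer that Figure 12 shows an artificial correlation because viral AUC also runs to discharge. The figure's title refers to maximum cumulative scores, and no window for a maximum FLU-PRO score is defined. A simulation under assumed stays of 8, 9, 10 and 12 days (55/20/15/10%) gave an induced Spearman correlation of only about 0.06.

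**Conclusion.** The point holds in a limited form. As written, the SAP sums FLU-PRO over a period whose length depends on shedding and symptoms, and it leaves out diary scores that discharged participants record on the same days. Relative to Day 8 discharge, the sum for a stay to Day 9 or 10 is higher by 12.5% or 25% at constant severity, by about 5% or 9% on the assumed declining course, and by nothing if nobody reports symptoms after Day 8. The direction follows from the definitions. The size rests on the assumed symptom courses and on a stay distribution that the documents do not give.

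The reach is one exploratory descriptive summary, plus any figure that plots the same sum. It would be wrong to infer that the attack rate or the choice of dose is affected: both rest on MJS and RT-PCR within Days 2 to 8. This is a desirable clarification, not a flaw in the primary analysis.

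**What to change.** In SAP 3.2.5 and the Table 43 note, define cumulative FLU-PRO (total and each domain score) as the sum of daily scores over Days 2-8 for every participant, whatever the discharge day. Use the same window wherever cumulative FLU-PRO is plotted (Figures 12 and 14), and say so in their notes. Do not substitute a mean per day over a variable stay.

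The cost is one changed derivation, with no new data. The downside is that symptoms after Day 8 drop out. On the declining course above, Days 9-15 contribute 0.63 of the 4.33 summed over Days 2-15, or 14.5%. If late symptoms are of interest, add a second row with the Days 2-15 sum for all participants, from the diary already collected.

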14.2.2 Immunogenicity Data Summary Tables

Table 49: Summary of Hemagglutination Inhibition Antibody Titers Against A/Texas/71/2017 (H3N2), clade 3C3a Virus, by Challenge Dose Group, Infection Status, and Study Day, ITT Population*

Study Day	Statistic	10 ⁴ TCID ₅₀ Challenge Virus (N=X)		10 ⁵ TCID ₅₀ Challenge Virus (N=X)		10 ⁶ TCID ₅₀ Challenge Virus (N=X)		Sham Inoculum (N=X)	
		Infected ^a	Uninfected	Infected ^a	Uninfected	Infected ^a	Uninfected	Infected ^a	Uninfected
Baseline	n	x	x	x	x	x	x	x	x
	GMT (95% CI) ^b	x.x (x.x, x.x)	x.x (x.x, x.x)	x.x (x.x, x.x)	x.x (x.x, x.x)	x.x (x.x, x.x)	x.x (x.x, x.x)	x.x (x.x, x.x)	x.x (x.x, x.x)
Day 8	n	x	x	x	x	x	x	x	x
	GMT (95% CI)	x.x (x.x, x.x)	x.x (x.x, x.x)	x.x (x.x, x.x)	x.x (x.x, x.x)	x.x (x.x, x.x)	x.x (x.x, x.x)	x.x (x.x, x.x)	x.x (x.x, x.x)
	GMFR (95% CI) ^b	x.x (x.x, x.x)	x.x (x.x, x.x)	x.x (x.x, x.x)	x.x (x.x, x.x)	x.x (x.x, x.x)	x.x (x.x, x.x)	x.x (x.x, x.x)	x.x (x.x, x.x)
	Seroconversion - % (95% CI) ^c	x.x (x.x, x.x)	x.x (x.x, x.x)	x.x (x.x, x.x)	x.x (x.x, x.x)	x.x (x.x, x.x)	x.x (x.x, x.x)	x.x (x.x, x.x)	x.x (x.x, x.x)
Day 15	n	x	x	x	x	x	x	x	x
	GMT (95% CI)	x.x (x.x, x.x)	x.x (x.x, x.x)	x.x (x.x, x.x)	x.x (x.x, x.x)	x.x (x.x, x.x)	x.x (x.x, x.x)	x.x (x.x, x.x)	x.x (x.x, x.x)
	GMFR (95% CI)	x.x (x.x, x.x)	x.x (x.x, x.x)	x.x (x.x, x.x)	x.x (x.x, x.x)	x.x (x.x, x.x)	x.x (x.x, x.x)	x.x (x.x, x.x)	x.x (x.x, x.x)
	Seroconversion - % (95% CI)	x.x (x.x, x.x)	x.x (x.x, x.x)	x.x (x.x, x.x)	x.x (x.x, x.x)	x.x (x.x, x.x)	x.x (x.x, x.x)	x.x (x.x, x.x)	x.x (x.x, x.x)
Day 29	n	x	x	x	x	x	x	x	x
	GMT (95% CI)	x.x (x.x, x.x)	x.x (x.x, x.x)	x.x (x.x, x.x)	x.x (x.x, x.x)	x.x (x.x, x.x)	x.x (x.x, x.x)	x.x (x.x, x.x)	x.x (x.x, x.x)
	GMFR (95% CI)	x.x (x.x, x.x)	x.x (x.x, x.x)	x.x (x.x, x.x)	x.x (x.x, x.x)	x.x (x.x, x.x)	x.x (x.x, x.x)	x.x (x.x, x.x)	x.x (x.x, x.x)
	Seroconversion - % (95% CI)	x.x (x.x, x.x)	x.x (x.x, x.x)	x.x (x.x, x.x)	x.x (x.x, x.x)	x.x (x.x, x.x)	x.x (x.x, x.x)	x.x (x.x, x.x)	x.x (x.x, x.x)
Day 57	n	x	x	x	x	x	x	x	x
	GMT (95% CI)	x.x (x.x, x.x)	x.x (x.x, x.x)	x.x (x.x, x.x)	x.x (x.x, x.x)	x.x (x.x, x.x)	x.x (x.x, x.x)	x.x (x.x, x.x)	x.x (x.x, x.x)
	GMFR (95% CI)	x.x (x.x, x.x)	x.x (x.x, x.x)	x.x (x.x, x.x)	x.x (x.x, x.x)	x.x (x.x, x.x)	x.x (x.x, x.x)	x.x (x.x, x.x)	x.x (x.x, x.x)
	Seroconversion % (95% CI)	x.x (x.x, x.x)	x.x (x.x, x.x)	x.x (x.x, x.x)	x.x (x.x, x.x)	x.x (x.x, x.x)	x.x (x.x, x.x)	x.x (x.x, x.x)	x.x (x.x, x.x)

Notes: n = Number of participants in the Intent-to-Treat population with available results; GMT = Geometric Mean Titer; GMFR = Geometric Mean Fold-Rise.

^a RT-PCR+ results reported on at least two days during the challenge period (Days 2 to 8).

^b Confidence Interval calculated based on the Student's t-distribution.

^c Exact binomial confidence interval calculated using the Clopper-Pearson methodology.

Similar Tables:

Table 50: Summary of Microneutralization Antibody Titers Against A/Texas/71/2017 (H3N2), clade 3C3a Virus, by Challenge Dose Group, Infection Status, and Study Day, ITT Population*

Table 51: Summary of Neuraminidase Inhibition Antibody Titers Against A/Texas/71/2017 (H3N2), clade 3C3a Virus, by Challenge Dose Group, Infection Status, and Study Day, ITT Population

Table 52: Summary of Anti-Hemagglutination Stalk Antibody Titers Against A/Texas/71/2017 (H3N2), clade 3C3a Virus, by Challenge Dose Group, Infection Status, and Study Day, ITT Population*

Table 53: Summary of Hemagglutination Inhibition Antibody Titers Against A/Texas/71/2017 (H3N2), clade 3C3a Virus, by Symptomatic Infection Status, and Study Day, ITT Population

Study Day	Statistic	Symptomatic and Infected (N=X)	Asymptomatic and Infected (N=X)	Symptomatic and Uninfected (N=X)	Asymptomatic and Uninfected (N=X)
Baseline	n	x	x	x	x
	GMT (95% CI) ^b	x.x (x.x, x.x)	x.x (x.x, x.x)	x.x (x.x, x.x)	x.x (x.x, x.x)
Day 8	n	x	x	x	x
	GMT (95% CI)	x.x (x.x, x.x)	x.x (x.x, x.x)	x.x (x.x, x.x)	x.x (x.x, x.x)
	GMFR (95% CI) ^b	x.x (x.x, x.x)	x.x (x.x, x.x)	x.x (x.x, x.x)	x.x (x.x, x.x)
	Seroconversion - % (95% CI) ^c	x.x (x.x, x.x)	x.x (x.x, x.x)	x.x (x.x, x.x)	x.x (x.x, x.x)
Day 15	n	x	x	x	x
	GMT (95% CI)	x.x (x.x, x.x)	x.x (x.x, x.x)	x.x (x.x, x.x)	x.x (x.x, x.x)
	GMFR (95% CI)	x.x (x.x, x.x)	x.x (x.x, x.x)	x.x (x.x, x.x)	x.x (x.x, x.x)
	Seroconversion - % (95% CI)	x.x (x.x, x.x)	x.x (x.x, x.x)	x.x (x.x, x.x)	x.x (x.x, x.x)
Day 29	n	x	x	x	x
	GMT (95% CI)	x.x (x.x, x.x)	x.x (x.x, x.x)	x.x (x.x, x.x)	x.x (x.x, x.x)
	GMFR (95% CI)	x.x (x.x, x.x)	x.x (x.x, x.x)	x.x (x.x, x.x)	x.x (x.x, x.x)
	Seroconversion - % (95% CI)	x.x (x.x, x.x)	x.x (x.x, x.x)	x.x (x.x, x.x)	x.x (x.x, x.x)
Day 57	n	x	x	x	x
	GMT (95% CI)	x.x (x.x, x.x)	x.x (x.x, x.x)	x.x (x.x, x.x)	x.x (x.x, x.x)
	GMFR (95% CI)	x.x (x.x, x.x)	x.x (x.x, x.x)	x.x (x.x, x.x)	x.x (x.x, x.x)
	Seroconversion % (95% CI)	x.x (x.x, x.x)	x.x (x.x, x.x)	x.x (x.x, x.x)	x.x (x.x, x.x)

Similar Tables:**Table 54: Summary of Microneutralization Antibody Titers Against A/Texas/71/2017 (H3N2), clade 3C3a Virus, by Symptomatic Infection Status, and Study Day, ITT Population****Table 55: Summary of Neuraminidase Inhibition Antibody Titers Against A/Texas/71/2017 (H3N2), clade 3C3a Virus, by Symptomatic Infection Status, and Study Day, ITT Population****Table 56: Summary of Anti-Hemagglutination Stalk Antibody Titers Against A/Texas/71/2017 (H3N2), clade 3C3a Virus, by Symptomatic Infection Status, and Study Day, ITT Population**

